5. DETERMINATION OF SAMPLE SIZE

It is estimated that the proportion of subjects who will achieve a vIGA-ADTM score of 0 or 1 and at least a 2-grade reduction from Baseline to Week 8 will be 45% for subjects receiving tapinarof compared with 25% for subjects receiving vehicle control, based upon the Phase 2 results. With 400 subjects randomized in a 2:1 ratio (267 subjects receiving tapinarof, and 133 subjects receiving vehicle control), this will provide 97.2% power for statistical significance (2-sided p <0.05). The power is calculated from a Fisher Exact sample size calculation. It is assumed that 15% of the subjects receiving tapinarof will be lost to follow-up by 8 weeks compared with 30% of the subjects receiving vehicle control. These subjects will be included in the primary analysis using the multiple imputation method.

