7. NOTATION OF TREATMENT GROUPS AND VISITS

Notation of treatment groups

The following notation of **treatment groups** will be used throughout the report:

Full Notation (as used in the study protocol)	Notation Used Throughout All Tables, Listings, and Figures
Tapinarof Cream 1%	Tapinarof Cream 1%
Vehicle	Vehicle Cream

Visit terminology

Visit	Notation Used Throughout All Tables, Listings, and Figures
Screening, Days -30 through Day -1, Visit V1	Screening
Baseline, Day 1, Visit V2	Baseline
Week 1, Day 8, Visit V3	Week 1
Week 2, Day 15, Visit V4	Week 2
Week 4, Day 29, Visit V5	Week 4
Week 8, Day 57, Visit V6 (End of Treatment)	Week 8
Week 9, Day 64, Visit V7 (End of Study/Follow-up) [1]	Week 9

Note: phone calls to assess AEs and concomitant medications, to review study drug application procedures, and to confirm subject's continued participation in the study will occur on Week 3 (Day 22) and Week 6 (Day 43).

[1] Subjects who choose not to participate in the OL-LTE study or who fail to qualify for participation in the OL-LTE study will complete a Follow-up Visit (Week 9 visit) approximately 1 week after the end of treatment in this study.

Analysis visits

Study days are measured from date of first dose of study medication. Study days corresponding to measurements are calculated as:

- Assessment date date of first dose + 1 if assessment date is on or after the date of first exposure of treatment.
- Assessment date date of first dose if assessment date is before the date of first exposure of treatment.

All efficacy and safety endpoints will be analyzed according to the nominal visits (i.e., actual visit) except for assessments collected on early termination and unscheduled visits. Early termination and unscheduled visits will be re-numbered to an analysis visit based on their windowed visits defined by actual study day. If more than one visit occurs within a single visit window, then the analysis will take the one closest to the target day. If the 2 visits are equidistant from the target day, the visit with later date and time will be used.

The following analysis visit windows will apply to early termination and unscheduled visits:

Analysis Visit	Target Day	Analysis Visit Window
Baseline	1	1
Week 1	8	Post first dose to Day 12
Week 2	15	Day 13 – Day 21
Week 4	29	Day 22 – Day 42
Week 8	57	Day 43 – Maximum (last day of treatment + 3 days, Day 59)
Week 9	64	>Maximum (last day of treatment + 3 days, Day 59)

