8. ANALYSIS SETS

The safety population will be used for the safety analyses and will include all randomized subjects who receive at least 1 application of study drug. Treatment assignment will be based on the treatment received.

The following subject populations will be used for efficacy analyses:

- The intent-to-treat (ITT) population will include all randomized subjects. Treatment assignment will be based on the randomized treatment.
- The per-protocol (PP) population will exclude ITT subjects with protocol deviations or other events that may impact the interpretation of the primary efficacy endpoint, regardless of whether the deviation(s) is considered major or minor. Exclusion criteria for the Per-protocol population may include:
 - Failure to meet the enrollment inclusion/exclusion criteria
 - Specified use of prohibited concomitant medication

Systemic Agents:

- Oral/systemic corticosteroids for >5 days
- Oral PDE4 inhibitors used for atopic dermatitis (e.g., roflumilast, apremilast); or other conditions if not on stable dose for period prior to and over course of the study
- Any oral immunosuppressive medication including cyclosporine, Imuran (azathioprine), methotrexate, tacrolimus, any Janus kinase inhibitor
- Injected IL4/13 blocking biologic including lebrikizumab, dupilumab
- Oral/systemic retinoids (e.g., alitretinoin), if not on a stable dose for period prior to and over course of the study
- Other injected monoclonal antibodies with potential impact on AD (omalizumab)
- Oral/systemic antihistamines for ≥ 3 days when used for skin conditions
- Oral/systemic antibacterials for ≥ 3 days when used for skin conditions
- Other investigational drug

Topical Agents:

- Topical immunomodulators on affected skin (other than transient <5
 days focal treatment for AESI) including topical corticosteroids, topical
 calcineurin inhibitors (Elidel, Protopic), topical PDE4 inhibitor
 (crisaborole/Eucrisa), coal car containing products
- Topical emollients containing keratolytics (including salicylic acid, urea) on affected skin (other than transient ≤7 days focal treatment for AESI)
- Topical antihistamines for ≥ 3 days when used for skin conditions
- Topical antibacterials limited to gentamicin and neomycin
- Other investigational drug
- Failure to be compliant with treatment regimen (compliance < 80%)
- Inclusion of scalp in efficacy assessment (see protocol section 5.1.5)

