10.4 Handling of Dropouts or Missing Data

Imputation of Missing Efficacy Data

The principal method for handling of missing data will be multiple imputation (MI). MI will be performed separately using estimand requirements (MI estimand) and without estimand requirements (MI non-estimand). MI estimand will be considered primary.

For the MI estimand analyses investigator assessments including vIGA-ADTM, EASI, %BSA based on data not collected at in-person visits (e.g., due to COVID-19 considerations) will be set to missing. Multiple imputation will be done as described in more detail below. Afterwards, using the MI estimand dataset, subjects who prematurely discontinue treatment due to an AE or lack of efficacy and subjects who use a specified prohibited medication prior to Week 8 will be considered a treatment failure at the time of treatment discontinuation or the date of initiation of prohibited medications for the primary and dichotomized secondary endpoints. For the continuous secondary endpoint of change from baseline BSA, BSA value will be set to the baseline value for the treatment failures specified above. For the MI non-estimand analyses, all visit assessments (including in-clinic and not in-clinic) will be included. Treatment failures will not be implemented as described previously for the MI estimand analyses.

For both the MI estimand and MI non-estimand analyses, 100 imputations will be generated using PROC MI of SAS. Fully Conditional Specification (FCS) model using the regression method will be used with the response (e.g., vIGA-ADTM score) at prior post-baseline visits, baseline vIGA-ADTM score, baseline age group, baseline value of the corresponding endpoint (for endpoints other than vIGA-ADTM score), and treatment group as covariates. The ROUND, MINIMUM and MAXIMUM options will be utilized to ensure imputed values are within appropriate ranges and precision. The seed to be used in all MI models is 20230421.

Two sets of MI datasets (MI estimand and MI non-estimand) will be generated for the vIGA-ADTM scores, EASI scores, %BSA, and PP-NRS results separately. Response status (Yes, No) will be derived from the imputed scores in each MI dataset. Analysis of each primary and secondary outcome will then be performed for each of the relevant MI datasets. The results of the 100 analyses will be transformed into a normal statistic and combined into a single analysis using PROC MIANALYZE.

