11. METHODS OF EFFICACY ANALYSIS

11.1 Primary Efficacy Analyses

The primary estimand of interest is the composite estimand in a patient population offered treatment with tapinar fcream, 1% as compared to vehicle. Interest is focused on the treatment

effect measured by the ratio of response rates at Week 8. The primary efficacy endpoint for treatment effectiveness is proportion of subjects who achieve vIGA-ADTM score of clear (0) or almost clear (1) and at least a 2-grade reduction from Baseline at Week 8. Subjects who prematurely discontinue treatment due to an AE or lack of efficacy and subjects who use a prohibited medication with significant impact on efficacy evaluations prior to Week 8 will be considered treatment failure as of the start of the intercurrent event. Discontinuing treatment due to adverse event or lack of efficacy will be based on data recorded on the End of Treatment eCRF. Analysis will be based only on data collected at in-person visits for investigator assessments.

Estimand Attribute	Description
Treatment	tapinar of cream, 1% compared to vehicle
Population	Intent-to-treat
Variable of interest	Proportion of subjects who achieve vIGA-AD TM score of clear (0) or almost clear (1) and at least a 2-grade reduction from Baseline at Week 8
Intercurrent event handling	Subjects who prematurely discontinue treatment due to an AE or lack of efficacy and subjects who use a prohibited medication with significant impact on efficacy evaluations prior to Week 8 will be considered treatment failure. Investigator assessments will only include data collected at inperson visits.
Summary measure	Ratio of response rates at Week 8

The primary efficacy comparison will test the following hypotheses:

- H₀: The proportion of subjects who achieve a vIGA-ADTM score of clear (0) or almost clear (1) and at least a 2-grade reduction from Baseline at Week 8 is equal between tapinar of cream, 1% and vehicle cream;
- H₁: The proportion of subjects who achieve a vIGA-ADTM score of clear (0) or almost clear (1) and at least a 2-grade reduction from Baseline at Week 8 is different between the tapinar of cream, 1% and vehicle cream.

The primary efficacy endpoint will be analyzed using a Cochran–Mantel–Haenszel (CMH) test stratified by vIGA-ADTM score at Baseline (vIGA-ADTM scores of 3 or 4) and age group (2-6 yrs, 7-11 yrs, 12-17 yrs, 18+ yrs) based on the ITT population using the MI estimand approach.

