A tipping point analysis will be done using vIGA-ADTM observed cases data. All possible combinations of the number of imputed successes (vIGA-ADTM score of clear (0) or almost clear (1) and at least a 2-grade reduction from Baseline at Week 8) by treatment group will be enumerated, accounting for baseline vIGA-ADTM and age group. CMH p-values will be computed for each combination and results will be summarized and displayed in a tipping point plot. If computational issues are encountered due to a large number of combinations, then alternative approaches will be utilized.

Supporting analyses of the primary endpoint will also be performed:

• in the PP population using the MI estimand dataset only.

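### The tipping point is specified on observed-cases data without the intercurrent-event failure rule or the in-person restriction, so as written it is not aligned with the primary composite estimand (minor)

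*SAP*

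**What the plan says.** **The estimand.** SAP 11.1 defines a composite estimand. Subjects who stop treatment for an adverse event or lack of efficacy, or who use a prohibited medication with significant impact on efficacy evaluations before Week 8, "will be considered treatment failure as of the start of the intercurrent event". The same section limits investigator assessments to in-person data.

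**Where the rules are applied.** SAP 10.4 implements both for the MI estimand data. Non-in-person scores are set to missing, imputation is run, and then the failure rule is applied: "Afterwards, using the MI estimand dataset, subjects who prematurely discontinue treatment due to an AE or lack of efficacy and subjects who use". The sentence goes on to name the medications concerned and makes all of these subjects failures. For the MI non-estimand analysis the rule is expressly switched off. For observed cases, SAP 10.4 says only that nothing is imputed.

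**The tipping point.** SAP 11.1 says: "A tipping point analysis will be done using vIGA-ADTM observed cases data". It goes on: "All possible combinations of the number of imputed successes" are to be enumerated by arm, with a CMH p-value for each. Neither the failure rule nor the in-person restriction is repeated. The supporting analysis that follows is to be done "in the PP population using the MI estimand dataset only", so the section does name a data source where one is meant.

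**Which scores can be observed.** SAP 7 says: "Early termination and unscheduled visits will be re-numbered to an analysis visit based on their windowed visits defined by actual study day". The Week 8 window opens on Day 43. Protocol 7.9 records vIGA-AD at the Early Termination visit. Protocol 4.6.1 makes withdrawal for prohibited medication optional. Protocol 6.6 allows vIGA-AD by video.

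**The concern.** The tipping point is the only planned analysis that varies the outcomes of missing subjects separately by arm. The plan itself expects unequal loss: "It is assumed that 15% of the subjects receiving tapinarof will be lost to follow-up by 8 weeks", against 30% on vehicle. A reader will use the plot to judge how far the missing outcomes must depart before the primary result is lost. That reading is only valid if the plot uses the same outcome definition as the primary analysis.

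On observed-cases data as written, three groups can be coded differently from the primary analysis:

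- **(a)** A subject who stopped for an adverse event or lack of efficacy and has no Week 8 score is treated as open and can be tipped to success.
- **(b)** A subject with an intercurrent event and an observed Week 8 response stays a success in every cell. This can happen through an Early Termination visit from Day 43, or through specified prohibited medication while remaining on study.
- **(c)** A video vIGA-AD score is kept, although the primary analysis sets it to missing.

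Two programmers could handle these groups differently and both claim to have followed the text.

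**Working it through.** **The plan's own figure.** SAP 5 states 97.2% power for 267 against 133 subjects, 45% against 25%, Fisher exact, two-sided 0.05. Exact enumeration gives 97.6%, and the continuity-corrected sample size formula at 97.2% power returns 133 vehicle subjects. The figure reproduces closely and is not in dispute.

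**Inputs for the illustration (SAP 5).**
- Missing at Week 8: 0.15 × 267 ≈ 40 on tapinarof; 0.30 × 133 ≈ 40 on vehicle.
- Observed: 227 and 93. Observed responders: 0.45 × 227 ≈ 102; 0.25 × 93 ≈ 23.
- Missing tapinarof subjects assumed to respond at 45%: 18 of 40.
- Numbers of event subjects are not in the documents and are assumed throughout.

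**Formula.** CMH statistic collapsed to one stratum, because no stratum counts are given:

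Q = (x₁ − n₁m/N)² / [n₁n₂m(N − m) / (N²(N − 1))]

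Here n₁ = 267, n₂ = 133, N = 400, x₁ is tapinarof responders and m is all responders. The tip is the smallest number of successes among the 40 missing vehicle subjects at which p ≥ 0.05.

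**As written.** x₁ = 102 + 18 = 120.
- 23 vehicle successes: m = 120 + 46 = 166, expected 110.805, variance 21.607, Q = 9.195² / 21.607 = 3.913, p = 0.048.
- 24 vehicle successes: m = 167, expected 111.4725, variance 21.644, Q = 8.5275² / 21.644 = 3.360, p = 0.067.
- The tip is 24 of 40 (60%).

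**Group (b): observed responders recoded as failures.** The as-written tip stays at 24. With estimand coding:

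| Recoded (tapinarof / vehicle) | p just before the tip | p at the tip | Tip of 40 |
|---|---|---|---|
| 0 / 0 | 0.048 | 0.067 | 24 |
| 1 / 1 | 0.040 | 0.056 | 24 |
| 2 / 2 | 0.047 | 0.066 | 25 |
| 2 / 0 | 0.047 | 0.066 | 23 |
| 5 / 0 | 0.039 | 0.055 | 21 |
| 8 / 0 | 0.045 | 0.063 | 20 |
| 0 / 4 | 0.048 | 0.067 | 28 |

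The as-written plot is too lenient when such subjects are mostly on tapinarof, and too strict when they are mostly on vehicle.

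**Group (a): event subjects with no Week 8 score.** Suppose some of the 40 missing per arm are event failures. As written, the grid has 41 × 41 = 1681 cells, of which 1009 (60%) keep p < 0.05 in favour of tapinarof. Fixing 25%, 50% or 75% of the missing as failures leaves 689 of 961 (72%), 401 of 441 (91%) or 121 of 121 (100%). The boundary does not move. With every missing tapinarof subject failing, the tip is 15 vehicle successes with none, 25% or 50% fixed, and it cannot be reached once only 10 vehicle subjects remain open. Every estimand scenario is already a cell of the as-written grid; the extra cells are ones that cannot occur.

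**Group (c).** The documents give nothing from which to size this.

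**The case against.** **Inheritance.** The tipping point is called a sensitivity analysis of the primary endpoint and sits in the section that defines the failure rule and the in-person restriction. MI non-estimand is the only analysis for which the SAP expressly switches the rule off. Inheritance is a reasonable reading. It is not a safe one: that same section also contains the MI non-estimand analysis, so being under the heading does not import the rule, and the adjacent per-protocol analysis names its estimand dataset explicitly.

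**Group (a) is harmless.** This stands. A reader might infer that the plan fails to stress-test the primary result at all, or point to an as-written tip falling from 60% (24/40) to 51% (27/53) when 13 event dropouts per arm join the open pool. That fall is largely a change of denominator. With the tapinarof event dropouts held as failures inside the same grid, the tip is again 24 successes.

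**Group (b) is narrow.** This largely stands. The Early Termination route needs someone who stopped from about Day 43 onward and was clear or almost clear with a two-grade drop; a lack-of-efficacy discontinuer would rarely qualify. The medication route is limited by the note in Protocol 4.6.1, which ties staying on study drug to medication judged not to interfere. SAP 8 itemises "Specified use of prohibited concomitant medication", but as a possible per-protocol exclusion. SAP 10.4 does not cite that list, so its overlap with the estimand's medications is unknown.

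**Material not available.** Appendix C and the table shells are not in the supplied text, nor is the example SAS code mentioned in the revision history. Any of these might show the intended handling.

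**Imputation order.** A reader might also infer that SAP 10.4 is wrong to impute first and apply the failure rule afterwards. The text is explicit and consistent, and event subjects are failures either way. Removing post-event scores before imputation is a modelling preference, and no change is asked for there.

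**Conclusion.** The point holds as a minor misalignment between one planned sensitivity analysis and the primary estimand. Following SAP 11.1 literally, observed Week 8 responders with an intercurrent event stay successes in every cell, and video scores are not excluded. Event subjects without a Week 8 score only make the grid stricter than it needs to be.

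The size cannot be determined from the documents. Under the assumptions above, one or two such responders in each arm leave the tip at 24 or 25 of 40, against 24 as written. Larger one-sided counts move it to between 20 and 28. These figures rest on a single stratum, assumed event counts and tapinarof missing outcomes at 45%.

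A reader might conclude that the plot is biased in favour of tapinarof, or that the primary result is in doubt. The documents support neither. The direction depends on which arm has the event responders, and the primary p-value, alpha and sample size do not depend on the tipping point.

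**What to change.** Change SAP 11.1 only. State that, before enumeration, subjects with a listed intercurrent event are set as non-responders and vIGA-AD scores not collected in person are set to missing, and that only the remaining missing Week 8 outcomes are varied.

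The cost is one sentence and a few program lines before unblinding, with no new data. Fixing event dropouts as failures also removes them from the enumeration, which helps with the computational difficulty that SAP 11.1 anticipates. If Appendix C or the table shells already specify this coding, it is enough to bring the text of SAP 11.1 into line with them.

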11.2 Secondary Efficacy Analyses

The dichotomized secondary endpoints will follow the same composite variable strategy estimand (MI estimand) as the primary analysis of the primary endpoint.

For PP-NRS, if any day of the 7-day period used to compute the average weekly PP-NRS score is on or after the date of the intercurrent event, then the response will be considered a failure for the estimand analysis starting at that visit.

[figure not shown]
Mean change in %BSA will be analyzed with an ANCOVA with factor of treatment and age group*vIGA-ADTM score as a categorical covariate and baseline %BSA as a continuous covariate. The age group*vIGA-ADTM score covariate cohort is as follows:

age group:	vIGA-AD TM score	age group* vIGA-ADTM score cohort
2-6 yrs	3	1
2-6 yrs	4	2
7-11 yrs	3	3
7-11 yrs	4	4
12-17 yrs	3	5
12-17 yrs	4	6
≥18 yrs	3	7
≥18 yrs	4	8

[figure not shown]
The standard MI procedures (Section 10.4) for ANCOVA will be followed. Least squared means of treatment difference (tapinarof – vehicle) along with the 95% CI will be reported. Change from baseline will be assigned to 0 in a manner corresponding to assignment of non-response for the dichotomized secondary endpoints for subjects who discontinue treatment due to an AE or lack of efficacy and subjects who use prohibited medication with significant impact on efficacy evaluations prior to Week 8.

[figure not shown]
The secondary efficacy endpoints will be tested sequentially using the MI estimand analyses. Testing will stop if non-significance (2-sided $p \ge 0.05$) is observed as described in Section 10.7.

[figure not shown]
11.3 Exploratory Analyses

12. PHARMACOKINETIC ANALYSES

All blood samples collected at Week 4 will be analyzed by the PK laboratory. Additionally, the PK laboratory will analyze Week 8 samples for subjects randomized to tapinarof cream, 1%.

12.1 Presentation of Plasma Concentrations

Individual plasma concentration results:

A raw data listing will be provided displaying the concentration as reported and the nominal and actual sampling times relative to start of dose administration. Results will be displayed using 3 significant digits. Listings will be sorted by treatment, subject, day, and time.

Summary statistics of plasma concentrations:

The plasma concentrations for each analyte will be summarized by treatment and the nominal time point at Week 4 and 8 (Days 29 and 57) using descriptive statistics (n, arithmetic mean, median, standard deviation (SD), minimum, and maximum. Additionally, plasma concentrations will be summarized by treatment group and nominal timepoint by (1) age cohort (2-6 yrs, 7-11 yrs, 12-17 yrs, and ≥ 18 yrs), (2) race (White, Asian, Black or African American and Other), (3) %BSA (<10% and ≥ 10 %), and (4) plasma tapinarof concentrations divided by baseline %BSA affected.

Exploratory analyses may include relationships of plasma concentrations with patient demographics, efficacy parameters, and/or TEAEs.

13. SAFETY ANALYSES

All safety analyses will be based on the safety population. No formal comparisons will be made for safety data.

